# **Exploratory Objectives:**

- 1) To evaluate the intraclass correlation (reliability) of hand-held POCUS for the assessment of second and third trimester fetal biometry
- 2) To assess the validity of hand-held POCUS in patients with different antenatal risk factors (SGA, Diabetes, and RFM)
- 3) To examine the efficiency of hand-held POCUS for second and third trimester assessment of fetal biometry
- 4) To determine the minimum sufficient sample size to detect a difference in measurements taken with

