#### **POCUS versus SUM**

#### 5.2. Outcome

The primary outcomes will be the acceptability and feasibility of point-of-care ultrasound to patients. This will be assessed as:

- 1) The number of patients approached who agree to participate (objective 1)
- 2) The response rate to the questionnaire (objectives 2 and 3)
- 3) The number of patients willing to undergo POCUS scans in the future as determined by the questionnaire responses (objective 2)
- 4) The number of unblinding episodes that occur (objective 4)

The exploratory outcomes will investigate the reliability and validity of the point-of-care ultrasound device. This will be assessed as:

- 1) For categorical data, Kappa coefficients demonstrating 90% agreement or greater (objectives 1 and 2)
- 2) For numerical data, ICC 0.9 or greater (objectives 1 and 2)
- 3) For continuous data (fetal biometric measurements), high level of agreement with Bland Altman, defined as ≥95% of the differences between the two measurement methods fall within the clinically acceptable range of ±3 to ±7 mm, depending on gestational age (objectives 1 and 2)
- 4) The difference in the mean time taken to perform each type of scan (POCUS and SUM) (objective 3)
- 5) The number of patients in whom fetal assessment could not be performed (objective 2)
- 6) Data from the feasibility study will inform the sample size calculation for the full randomized controlled trial by providing estimates of outcome variability, effect size, and recruitment parameters necessary for a power analysis (objective 4)

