### 6. STUDY DESIGN AND METHODS OF DATA COLLECTION

This will be a feasibility study involving both qualitative and quantitative data developed in line with current guidance (19, 20). This feasibility study has been designed to establish the feasibility and acceptability of a future randomised controlled trial (RCT). It will involve pseudo-anonymised data collection from pregnant patients. This study will not involve an alteration to the standard care of enrolled patients.

Participants will undergo ultrasound with POCUS with a probe frequency of 3-5 MHz. The same probe model (Vscan Air CL, GE Voluson, available for routine clinical use for presentation scanning at LWH) will be used for all POCUS scans to limit variability in image quality. This model utilises a personal mobile device or tablet for image display and saves images which can be uploaded to a secure server. Measurements of fetal head circumference (HC), abdominal circumference (AC), and femur length (FL) will be taken with both devices and incorporated into the Hadlock EFW calculation. (21). Patients will also undergo ultrasound with a standard ultrasound machine (standard care). While performing the standard ultrasound, the PI will be blinded to the measurement value by covering the area of the screen where the measurement number appears with an opaque card. Both scans will be performed by the same sonographer (study PI) to limit inter-observer variability. The results of these scans will be examined using the statistical analysis as detailed below. Time taken to obtain measurements will be obtained for both methods and compared.

Clinical data will also be collected. This will consist of maternal and fetal details including maternal body mass index (BMI), antenatal risk factors, and the gestational age at the time of the scan.

Ultrasound findings and clinical measurements to be collected prospectively are illustrated in Appendix 1.

The qualitative component will address the primary objective and secondary objective 4. Participants will be asked to fill in an experience questionnaire following the ultrasounds. This questionnaire will evaluate their perception/satisfaction with the POCUS scan. Data for the qualitative component assessing acceptability will be obtained from the responses to the questionnaire. Participants will be provided either a paper-based or online questionnaire hosted at RedCap

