#### 10. STATISTICS AND DATA ANALYSIS

### 10.1 Sampling

All pregnant patients attending Liverpool Women's Hospital Trust (diabetes antenatal clinic, fetal medicine unit growth clinic, maternity assessment unit with reduced fetal movements, admitted in antenatal ward with reduced fetal movements) will be considered to take part in this study.

As this is an exploratory study and no hypothesis testing is planned a formal sample size calculation has not been performed.

We will aim to include 60 patients per cohort. There will be three cohorts, so the total number of patients will be 180, and the number of scans performed 360. The sample size estimation was determined by the study team including the statistician because this is an exploratory study with a binary primary outcome (acceptable vs non-acceptable). A review of feasibility studies by Totton et al. (22) evaluated three studies of sample size estimations. The most recent of these studies was by Teare et al. (23), who recommend 60 participants per arm for feasibility studies with binary outcomes. 60 participants per cohort will generate sufficient results for feasibility and acceptability to achieve the proposed outcomes.

This sample size will also provide sufficient data for analysis of the secondary outcomes. As these are concerned with the level of agreement between the two ultrasound modalities, we will use Bland-Altman limits of agreement. Studies using this method rarely include sample size calculations, with an average sample size of 65.(24) The overall assessment of the devices from the combined three groups will involve a total sample of 180 paired scans.

Diabetes: The Diabetes antenatal clinic at LWH runs once a week on Tuesdays and sees between 20-40 patients per week. During a six-month period, this will equate to around 750 patients.

SGA: The Growth clinics at LWH run twice a week on Mondays and Thursdays and see roughly six patients per clinic. During a six-month period, this will equate to around 300 patients.

RFM: Patients present with RFM regularly to MAU at LWH. Around four patients per day will present. In a six-month period, this will equate to around 700 patients. The PI will aim to recruit from this clinical area weekly on Fridays.

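### The Bland-Altman criterion is a ±3 to ±7 mm range with no gestation-to-limit rule, shared by HC, AC and FL and read as a bare percentage, so it cannot be applied as written

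*Protocol*

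**What the plan says.** Protocol section 5.2, exploratory outcome 3, sets the benchmark "For continuous data (fetal biometric measurements), high level of agreement with Bland Altman", and defines it as "≥95% of the differences between the two measurement methods fall within the clinically acceptable range of ±3 to ±7 mm, depending on gestational age". Section 6 names the parameters: "Measurements of fetal head circumference (HC), abdominal circumference (AC), and femur length (FL) will be taken with both devices". It also says that the data collected include "antenatal risk factors, and the gestational age at the time of the scan". The exploratory objectives in section 5.1 cover the second and third trimesters. No section assigns a limit to a gestation or a separate limit to a parameter.

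Section 10.2 plans a mean difference with 95% confidence intervals, and Bland-Altman plots whose limits of agreement are to be inspected by eye. It names no interval for those limits or for the share of differences in band.

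Exploratory outcome 5 is a separate count: "The number of patients in whom fetal assessment could not be performed (objective 2"). The protocol does not say how such patients enter outcome 3.

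On numbers, section 10.1 says "We will aim to include 60 patients per cohort", with three cohorts, and adds: "This sample size will also provide sufficient data for analysis of the secondary outcomes". The support offered is the average size of published agreement studies (65), not a precision figure.

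**The concern.** A pass threshold works only if two analysts with the same data would reach the same answer. Here they need not. Each scan needs a limit between 3 and 7 mm, and the protocol does not say which. Section 10.2, whose subheading presents it as the analysis plan, does not supply one either.

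The band is also absolute. A limit of L mm on a structure of size M is a tolerance of 100 × L/M percent. One L shared by a long bone and two circumferences therefore means a different relative tolerance for each, and the verdict reflects structure size as well as device performance.

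Finally, the threshold is compared with an observed percentage that is imprecise at 60 per cohort. What is at stake is the study's statement on POCUS validity, and its answer to feasibility objective 3, which asks whether the outcome measures are suitable for assessing reliability.

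**Working it through.** **Inputs.** From the protocol: 95% threshold and ±3 to ±7 mm band (5.2); 60 per cohort, three cohorts (10.1). Assumed, because the documents give no figure: normal differences, zero bias unless stated, SD of differences from 1 to 5 mm.

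**1. The plan's own figure.** 3 × 60 = 180 patients; 180 × 2 = 360 scans. Both agree with section 10.1. There is no precision or power figure for outcome 3 to reproduce.

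**2. Largest SD that meets the rule.** With zero bias, 95% of differences lie within ±L when SD ≤ L/1.96.
- ±3 mm: 3/1.96 = 1.53 mm.
- ±7 mm: 7/1.96 = 3.57 mm.

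Any gestational mapping between 3 and 7 mm gives a share between those at the two edges. Below 1.53 mm the expected share reaches 95% under every mapping, and above 3.57 mm under none. Between them it depends on the mapping.

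**3. Size of the difference.** Share in band = P(|d| ≤ L). A cohort of 60 passes with at least 57 in band (0.95 × 60 = 57), so P(pass) is a binomial tail.

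| Assumed SD (mm) | Share within ±3 | P(pass), n = 60 | Share within ±7 | P(pass), n = 60 |
|---|---|---|---|---|
| 1.0 | 99.7% | about 100% | about 100% | about 100% |
| 2.0 | 86.6% | 3.3% | 99.95% | about 100% |
| 2.5 | 77.0% | 0.02% | 99.5% | 99.97% |
| 3.0 | 68.3% | about 0% | 98.0% | 97.0% |
| 5.0 | about 45% | about 0% | about 84% | 0.8% |

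A bias of 1 mm does not change the picture: at SD 2.5 mm the shares are 73.3% and 99.1%.

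**4. Precision of the observed share.** Exact (Clopper-Pearson) 95% intervals at the minimum passing count:
- 57/60 = 95%: 86.1% to 99.0%.
- 171/180 = 95%: 90.7% to 97.7%.

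If the true share is 90%, the rule is still met 13.7% of the time at n = 60 and 1.2% at n = 180. Requiring the lower confidence limit to reach 95% would not be workable: even 60/60 has a lower limit of 0.025^(1/60) = 94.0%, and the pooled sample would need 177/180.

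**5. Precision of each limit of agreement.** Half-width = t × SD × √(1/n + 1.96²/(2(n − 1))).
- n = 60: 2.00 × √(0.01667 + 0.03256) = 2.00 × 0.2219 = 0.44 SD.
- n = 180: 1.97 × √(0.00556 + 0.01073) = 1.97 × 0.1276 = 0.25 SD.

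**6. Measurements that could not be obtained (illustration).** Suppose 6 of 60 POCUS measurements are unobtainable. Among the 54 pairs, 52/54 = 96.3% meets the rule, while 52/60 = 86.7% of patients had an in-band result. If the 6 count as outside the limit, the best possible result is 54/60 = 90%, which fails. The protocol does not say which denominator applies.

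**The case against.** The strongest reply is that the outcome is exploratory, no hypothesis test is planned, and no primary feasibility outcome depends on this rule. The reference to gestational age shows that a mapping is intended, gestation is recorded, and an analysis plan that is not shown may hold the mapping, the intervals and the handling of missing pairs. Neither uniform edge is what the protocol describes, and the SDs are assumed.

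Much of this stands and limits the severity. It does not remove the point: the protocol chose to state a threshold, and what it states cannot be applied and makes no distinction between parameters. The two edges serve only to bracket whatever mapping is intended.

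Some stronger readings are tempting but not supported:
- **That failed scans are excluded to flatter agreement.** No section says so. Outcome 5 reports failures openly and does not name POCUS. The protocol is silent on the denominator, no more.
- **That this is the only validity criterion.** Section 5.2 also sets an ICC of 0.9 or more and a kappa benchmark. The ICC criterion for numerical data can cover estimated fetal weight, which a millimetre band cannot.
- **That FL will pass while HC and AC fail.** The documents give no measurement error by parameter. Only the unequal relative tolerance is certain.
- **That section 10.2 assumes constant spread.** It does not say so, and counting differences inside a band needs no such assumption.
- **That the limit will be chosen after the results are known.** The text leaves room for this but does not show it.

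**Conclusion.** The point holds in this form: outcome 3 fixes a pass criterion that cannot be applied as written, because the range has no gestational cut-points and the same absolute band covers HC, AC and FL. With zero bias and normal differences, the limit chosen decides the verdict for an SD of differences between 1.53 and 3.57 mm. At about 1 mm or at 5 mm it makes no difference. This dependence comes from the unmapped band alone.

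Separately, the bare percentage is imprecise at the planned sizes, so the sufficiency statement in section 10.1 has no precision figure behind it. The error rates in the working describe how the benchmark behaves; they are not a reason to turn it into a test. Because the outcome is exploratory, severity is minor to moderate.

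**What to change.** Before the paired differences are looked at:

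1. In section 5.2, replace the range with one pre-specified limit per parameter, either as a percent difference or as a parameter-by-gestation table. The clinical team should set the values.
2. Report the share in band and the limits of agreement with 95% confidence intervals, for each cohort and pooled. A pooled result alone would not serve exploratory objective 2 (validity across SGA, diabetes and RFM) or the within-group analysis in section 10.2.
3. Beside the criterion, show the number of measurements obtained with SUM but not with POCUS, and add a sensitivity analysis counting these as outside the limit. Restricting the count to cases where SUM succeeded avoids penalising POCUS when neither device could measure. Keep outcome 5 as it is.
4. In section 10.1, replace the sufficiency statement with the precision achieved: each limit of agreement to about ±0.44 SD at n = 60 and ±0.25 SD at n = 180.

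The cost is protocol wording and one table; no new data are needed, since gestation and all three parameters are already collected. The downside is that the criterion may be harder to meet.

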#### 3. RATIONALE FOR CURRENT STUDY

Increasing demand for ultrasound-based fetal growth surveillance is driven by the growing body of evidence implicating fetal growth restriction (FGR) and small for gestational age (SGA) as common causes of stillbirth, and a significant policy-based push toward reducing stillbirth rates at a national scale.

Patients at higher risk of FGR are identified following a risk assessment based on maternal characteristics and previous pregnancy outcomes, and are invited to undergo ultrasound assessment of fetal growth at regular intervals throughout the pregnancy (usually three to four weeks apart)(15). A cohort of these patients have risk factors that can make ultrasound assessment more challenging, including increased maternal body mass index (BMI) and diabetes leading to excess of amniotic fluid. Around one in 20 women who give birth in the UK have diabetes in pregnancy, either pre-existing or developed during the pregnancy. (16) Patients with diabetes and diagnosed SGA fetuses are required to attend more frequent scan appointments to ensure the fetal growth and wellbeing remains satisfactory (every two weeks or more if FGR is suspected). (17) Point-of-care devices are attractive to NHS services as they are more affordable than standard ultrasound machines, however it is unclear at present whether this is acceptable and feasible to deliver with training and image quality.

Patients presenting to the Maternity Assessment Unit (MAU) at or after 26 weeks of gestation with concerns regarding reduced fetal movements (RFM) in pregnancy represent a group with evolving risk for FGR. These patients are routinely offered a computerised CTG (cCTG) and an ultrasound scan assessment of fetal wellbeing comprising biometry, amniotic fluid volume assessment, and umbilical artery doppler studies. In our hospital, patients presenting with RFM at 39 weeks of gestation or greater are offered delivery via induction of labour or caesarean section and will only undergo ultrasound assessment in the event they decline delivery. As such, patients at 39 weeks or greater presenting with RFM will not be approached for this study.

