### 10.2 Data Analysis

### Data analysis and statistical analysis plan

Data arising from the questionnaires will be analysed in Microsoft Excel and will be reported using descriptive summary statistics, mean, medians, and counts (i.e. "54% of participants were satisfied with the POCUS scan").

Acceptability will be assessed using descriptive summary statistics, mean, medians, counts, and corresponding measures of variability.

Data will be analysed using SPSS (Statistical Package for the Social Sciences, IBM, Armonk NY).

The statistical methods have been chosen in collaboration with and at the advice of a University of Liverpool statistician ([name]) to ascertain agreement between the two methods of scanning (POCUS and SUM), and to enable appropriate statistical analysis of the proposed sample. Within each group we will use interclass correlation coefficients (ICC) and Spearman correlation coefficients (SCC) to check how closely the two methods agree by looking at the agreement between the paired measurements. Intraclass correlation coefficients measure how similar the measurements from the two methods are, indicating reliability or consistency for continuous variables. As the ICC approaches 1 (0.9 or greater), the greater the level of agreement. For this study, an ICC of 0.9 or greater will be considered a high level of agreement and indicate

increased reliability of the Vscan device.

To assess for difference in the scan duration, the mean scan time, median and interquartile ranges will be used. We will examine for correlation between the continuous variables of BMI and scan time with both POCUS and standard ultrasound. Calculation of a correlation coefficient will be performed with Spearman's correlation test.

Kappa coefficients measure agreement for categorical outcomes, such as assessments of fetal presentation or amniotic fluid levels. Values  $\leq 0$  indicate no agreement, 0.01–0.20 as none to slight, 0.21–0.40 as fair, 0.41–0.60 as moderate, 0.61–0.80 as substantial, and 0.81–1.00 as almost perfect agreement. These methods will be used to check for similarity within the methods (POCUS or SUM). This will ensure the measurements taken by the methods themselves are consistent.

Calculating the mean difference and 95% confidence intervals will provide estimate of any offset between two devices. Bland-Altman plots with limits of agreement will also provide a visual indication of the level of agreement between the two devices.

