# Measurements

POCUS: Fetal heartbeat, presentation, liquor volume (MVP), HC (mm), AC (mm), FL (mm), Umbilical Artery EDF, Placental location, EFW (g), Scan duration (HH:MM:SS)

SUM: Fetal heartbeat, presentation, liquor volume (MVP), HC (mm), AC (mm), FL (mm), Umbilical Artery EDF & PI, Placental location, EFW (g), Scan duration (HH:MM:SS

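### Estimated fetal weight has no agreement limit in its own unit and SGA status is not compared between devices, so POCUS can meet the millimetre and ICC criteria yet disagree with SUM on SGA

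*Protocol*

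**What the plan says.** Exploratory objective 2 (Protocol 5.1) is "To assess the validity of hand-held POCUS in patients with different antenatal risk factors (SGA, Diabetes, and RFM". Section 3 explains the demand for these scans by evidence on "fetal growth restriction (FGR) and small for gestational age (SGA) as common causes of stillbirth".

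Section 5.2 ties three agreement criteria to this objective:
- "For categorical data, Kappa coefficients demonstrating 90% agreement or greater (objectives 1 and 2"
- "For numerical data, ICC 0.9 or greater (objectives 1 and 2"
- Bland-Altman agreement for fetal biometry, with at least 95% of differences to "fall within the clinically acceptable range of ±3 to ±7 mm, depending on gestational age (objectives 1 and 2"

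It also counts the patients in whom assessment could not be performed.

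Section 6 says that HC, AC and FL "will be taken with both devices and incorporated into the Hadlock EFW calculation". Appendix 14.1 lists EFW in grams for both devices (for POCUS: "Umbilical Artery EDF, Placental location, EFW (g), Scan duration (HH:MM:SS"). The only SGA item in that appendix is whether the fetus was known to be SGA before the scan, which is not a result from either device.

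Section 10.2 plans ICC within each group, mean differences with 95% confidence intervals, and Bland-Altman plots with limits of agreement. It does not restrict these to HC, AC and FL. On categorical data it says: "Kappa coefficients measure agreement for categorical outcomes, such as assessments of fetal presentation or amniotic fluid levels".

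**The concern.** The three lengths are measured in order to be combined into a weight, and that weight for gestation is what places a fetus above or below an SGA line. The plan fixes a clinical limit for the lengths and none for the weight. No document text derives SGA status from each device or compares it.

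Two features make the gap matter. Errors in HC, AC and FL that each stay inside the limit combine in EFW, and a fixed millimetre error is proportionally large for the short femur. ICC, the one numerical threshold that does reach EFW, depends on how varied the fetuses are. Most of the variation in EFW in this sample will come from gestation, which says nothing about whether a fetus is small for its gestation.

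At stake is the answer to exploratory objective 2. It could look favourable on every numerical criterion and leave agreement on SGA unexamined. Feasibility objective 3 (are the outcome measures suitable?) and exploratory outcome 6 (inputs for the future trial) would lack the same information.

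**Working it through.** **The plan's own figure.** 3 cohorts × 60 = 180 patients and 180 × 2 = 360 scans, as section 10.1 states. The ±3 to ±7 mm range comes with no derivation, so it cannot be checked.

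**Assumed inputs (the protocol gives none).**
- Formula: log10 EFW = 1.326 − 0.00326·AC·FL + 0.0107·HC + 0.0438·AC + 0.158·FL, in cm.
- Gestation uniform over 26 to 39 weeks. Section 3 gives these bounds for reduced fetal movements; they are taken here for all cohorts.
- Median EFW rising log-linearly from 900 g to 3,400 g.
- Between-fetus SD at a given gestation of about 12%.
- SGA defined as EFW below the 10th centile for gestation by SUM.

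**Step 1: from millimetres to EFW.** Take HC 285, AC 250 and FL 58 mm, giving EFW 1,478 g. All three lengths short by 3 mm change EFW by −7.5%; all three short by 7 mm change it by −16.8%. FL alone short by 7 mm gives −11.6%. These are worst cases, with every error in one direction at the limit.

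**Step 2: why ICC passes.** On the log scale with no bias, ICC = V / (V + s²/2), where V is the variance between fetuses and s the SD of the device difference. Take s = 0.06.
- At a fixed gestation, V = 0.12² = 0.0144, so ICC = 0.0144 / (0.0144 + 0.0018) = 0.89. This fails the 0.9 threshold.
- Over 26 to 39 weeks, gestation adds [ln(3400/900)]²/12 = 1.329²/12 = 0.147. ICC = 0.1616 / (0.1616 + 0.0018) = 0.99. This passes easily.

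The device error is the same in both lines.

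**Step 3: SGA classification at the same errors** (400,000 simulated pairs, no bias, spread 12%):

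| SD of EFW difference | EFW ICC | SGA kappa | SUM-defined SGA missed | All fetuses reclassified |
|---|---|---|---|---|
| 4% | 0.994 | 0.75 | 18% | 4.8% |
| 6% | 0.987 | 0.64 | 23% | 7.3% |
| 8% | 0.977 | 0.54 | 28% | 9.8% |

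With a spread of 10% or 13% instead, kappa over these errors runs from 0.48 to 0.77.

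**Step 4: errors that just meet the mm criterion.** HC, AC and FL errors are independent and unbiased, with exactly 95% inside the limit, and are passed through the formula:

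| Limit | 95% of EFW differences | EFW ICC | SGA kappa | Missed | Reclassified |
|---|---|---|---|---|---|
| 3 mm | −5% to +5% | 0.998 | 0.84 | 12% | 2.9% |
| 3 rising to 7 mm with gestation | −8% to +8% | 0.993 | 0.75 | 18% | 4.7% |
| 7 mm | −11% to +13% | 0.989 | 0.66 | 22% | 7.0% |

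In all three rows the ICCs for HC, AC and FL are also at least 0.90. If the middle row also has an upward bias of half the limit, with 95% of differences still inside it, mean EFW rises by 5.8%, kappa falls to 0.58 and 56% of SUM-defined SGA is missed. The EFW ICC is then 0.985, and the lowest component ICC (FL) is 0.934.

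**Step 5: precision of the added comparison.** With 90% observed agreement, the 95% Wilson interval is about 80% to 95% for 54/60 and about 85% to 94% for 162/180.

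**The case against.** The strongest reply is that EFW is not left out. It is numerical, so the ICC threshold covers it, and the mean differences and Bland-Altman plots in section 10.2 are not confined to the three lengths. That stands. A reader might infer from the mm limit that validity in SGA is judged on lengths only, and section 5.2 does not support that reading. What remains is that the plots carry no acceptable limit for EFW, and that the ICC threshold is easily met for the reason in step 2.

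The kappa examples are introduced as examples, so an SGA category could be added. That also stands, but none is named or collected by device.

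A reader might also infer that a device meeting the mm limit would be declared valid. The protocol has no such rule: meeting it is called a high level of agreement, in a feasibility study without hypothesis tests and without change to care.

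Derived variables and extra tables are often left to an analysis plan, which may exist. This lowers the weight of the point. It does not remove it, because the acceptance criteria themselves are fixed in the protocol.

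Finally, the size rests on assumed inputs, the same-direction shifts in step 1 are extreme, and SGA yes/no is not shown to be the result acted on in every cohort. All fair. At 3 mm without bias, kappa of 0.84 is almost perfect on the protocol's own scale.

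**Conclusion.** The point holds in this form: for exploratory objective 2, EFW is judged at most by ICC of 0.9 or more and by Bland-Altman plots without a limit. The one clinical limit is in millimetres and cannot apply to grams, and SGA status is not compared between devices. POCUS could therefore meet the mm and ICC criteria and still classify SGA differently from SUM.

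With no bias and EFW error SDs of 4% to 8%, EFW ICC is about 0.975 to 0.994 with SGA kappa about 0.55 to 0.75, and about 5% to 10% of all fetuses are reclassified. With 3 mm limits and no bias, agreement is good. These figures depend on the assumed formula, spread, gestation range and 10% SGA proportion. They show what the criteria allow and do not predict how this device will perform.

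This is a worthwhile improvement to exploratory outcomes. It does not touch the primary feasibility and acceptability outcomes.

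**What to change.** Add two summaries to the exploratory outcomes for objective 2, using the EFW and gestation already recorded:

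1. A Bland-Altman analysis of the percentage EFW difference, 100 × (POCUS − SUM) / mean of the two, with 95% confidence intervals for the limits of agreement.
2. A descriptive cross-table of SGA yes/no by POCUS against SUM, using the centile standard the hospital already applies, which the protocol should name. Report it mainly pooled over the 180 pairs, with cohort counts shown. Give kappa, the numbers missed and over-called by POCUS relative to SUM, and confidence intervals.

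Add one sentence saying that meeting the mm or ICC criterion alone is not evidence of agreement on SGA classification.

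No extra scans or patients are needed. If the chosen standard needs variables beyond EFW and gestation, check that the CRF holds them. The price is wide intervals, sparse cells within cohorts (probably few non-SGA fetuses in the SGA cohort and few SGA fetuses elsewhere), and a result that may look less favourable to POCUS.
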